To determine whether cholinesterase inhibitors and memantine can slow the progression of disease in DAT subjects, we will use HDBM-LD and LCDM to compare the rate of change in the neuroanatomical measures listed above in three groups – 1) untreated DAT subjects, 2) DAT subjects treated with donepezil alone, and 3) DAT subjects treated with the combination of donepezil and memantine. Past, present and future subjects recruited from the ADRC as well as the Memory Diagnostic Center (MDC) at Washington University will be used for this study, and the period of treatment will be two years. Due to ethical considerations (see Research Design and Methods), drug treatment will be naturalistic and open label. **(Hypothesis 2: The rate of decreasing hippocampal and cortical volumes, thinning of the cingulate and parahippocampal cortices, and changing hippocampal shape will be equal in DAT subjects that are untreated and in DAT subjects that are treated with donepezil alone, but greater than the rate of volume loss, thinning and hippocampal shape change in DAT subjects that are treated with the combination of donepezil and memantine.)**

BACKGROUND

Cholinesterase Inhibitors as Treatments for DAT

Several cholinesterase inhibitors are now commercially available for the treatment of DAT, and have been shown to have at least ameliorative effects on the symptoms of DAT, including memory loss (Corey-Bloom, et al, 1998; Davis, et al. 1992; Farlow, et al, 1992; Knapp, et al, 1994; [name], et al, 1998; Rogers, et al., 1998; Rogers and Friedhoff, 1996; Thal, et al, 1996; Wilcock and Wilkinson, 1996). Cholinergic projections from the nucleus basalis are dispersed widely throughout the brain, and include the hippocampus, parahippocampal gyrus, cingulate gyrus and other neocortical areas. However, because of the central role played by the hippocampus and structures related to it in memory (Zola-Morgan and Squire, 1993), and the high frequency with which these structures are affected early in the course of Alzheimer's disease (Hyman, et al, 1984 and 1987; Arnold, et al, 1991; Gomez-Isla, et al, 1996; Berg, et al, 1998), these structures may be especially involved in symptom production and treatment response in subjects with DAT.

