Computerized methods for MR image analysis are being increasingly applied to the problem of identifying early forms of AD and other neuropsychiatric diseases (Iosifescu, et al, 1997; Thompson, et al, 1997; Ashburner, et al, 2003). We have recently completed several studies of the hippocampus using one of these methods (i.e., HDBM-LD) in subjects with very mild DAT, showing that hippocampal shape and volume can be used to discriminate DAT and control subjects (Csernansky, et al, 2000; Wang, et al, 2003) and that antemortem hippocampal volume predicted post-mortem tangle density in the hippocampus (Csernansky, et al, 2004). The results of these studies indicate that subjects with very mild DAT symptoms have highly characteristic shape deformations of the hippocampus as well as substantial hippocampal volume losses. These methods also hold promise for improving our capacity to study disease progression in DAT patients during drug treatment. In drug treatment studies, one is chiefly interested in assessing the degree of change within individuals. This problem is ideally addressed by methods that can transform one MR scan (i.e., at baseline) onto another (i.e., after drug treatment), thus quantifying subtle changes in neuroanatomical volumes and shapes. Fox and colleagues have performed a number of studies of this kind in subjects with and without DAT using a methodology called voxel compression mapping (VBM) (Fox, et al, 1996 and 2001; Fox and Freeborough, 1997; Freeborough and Fox, 1998). Also, this group has shown compelling evidence that VBM as compared to conventional manual volumetry significantly reduces the sample size required to detect the effects of drug treatment in patients with DAT (Fox, et al, 2000). During the first funding period of this project, we used HDBM-LD to compare patterns of change in hippocampal volume and shape in untreated patients with very mild DAT and non-demented controls (Wang, et al, 2003). In this study, we demonstrated that hippocampal shape change and the rate of volume loss provided complementary information for distinguishing subjects with DAT from the non-demented controls.

Clinical Significance of the Proposed Studies

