There was also a group difference in the rate of progression of hippocampal shape deformity. The first 12 eigenvectors explained 75% of the variance in hippocampal shape, and using these 12 eigenvectors as variables in a MANOVA, we found a significant group effect ($F = 2.66$, $df = 12,31$, $p = 0.014$; effect size = 2.0). In a follow-up logistic regression analysis, the combination of eigenvectors 1, 2, 4, and 11 were found to be optimally useful for discriminating the patterns of hippocampal shape change in the two groups of subjects ($\chi^2 = 19.4$). Using these four eigenvectors, a significant group x time interaction was found ($F = 7.81$, $df = 4,39$, $p < 0.008$), and in a “take-one-out” discriminant function analysis, 22 out of 26 (84.6%) CDR 0 subjects and 15 out of 18 (83.3%) CDR 0.5 subjects were correctly classified. When hippocampal volume change was included in this logistic regression analysis, only eigenvectors 2, 4, and 11 were selected ($\chi^2=20.1$) (eigenvector 1 was again correlated with the change in hippocampal volume across subject groups - $r = -0.75$, $p < 0.0001$). Visualization of the changes in the shape of the hippocampus in the two groups revealed that areas of inward deformities over time were more widespread in the CDR 0.5 than in the CDR 0 subjects (see Figure 2).

Hippocampal Shape Predicts Response to Donepezil

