Recently, we have adapted these methods to specifically assess the rate of change in hippocampal shape over time (Wang, et al, 2003). From the pairs of MR images collected at different time points, the assessment of a change in the shape of the hippocampus over time is accomplished by mapping the transformations from the first time point onto the second time point via rigid-motion registration (rotation and translation). If no change in the shape of the hippocampus has occurred, the result of this transformation is an identity map (modulo rotation and translation). Conversely, any shape change that has occurred is defined as the deviation of the result of the transformation away from this identity map. To compare shape change in different groups of subjects, the covariance of the resulting transformation vector fields across all subjects is used, and shape change is assessed in each group by 1) obtaining a set of eigenvectors via the singular value decomposition of the covariance matrix, 2) computing coefficients associated with these eigenvectors for each subject, and 3) performing a MANOVA using the eigenvectors across all subjects. A post-hoc logistic regression is used to determine which of the eigenvectors are most discriminating of the groups being compared. Since the covariance of the shape change vector fields is empirical, repeat neuroanatomical data from nondemented (CDR 0) subjects are required in order to account for “normal” shape change during the analysis of shape change associated with DAT and its treatment.

f. Methods for Labeled Cortical Depth Mapping (LCDM) of the Parahippocampal and Cingulate Gyri

When the brain structure of interest is a subregion of the cerebral cortex (e.g., cingulate or parahippocampal gyrus), it is first necessary to create a segmentation of the various tissues (i.e., gray matter, white matter, and CSF) within that portion of the MR dataset, and in relationship to the geometry of the neocortex. We have recently developed specific algorithms for this purpose (see Figure 5).

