Variables to assess changes in structural volume, thickness, and shape (for the hippocampus) will be generated as described above. Bivariate correlations between changes in clinical and neuroanatomical variables will be estimated using non-parametric statistics (Spearman's rho). To assess whether observed bivariate relationships are independent of each other, a stepwise multiple regression model will be developed including all independent neuroanatomical variables and slope values for the CDR sum-of-boxes scores as the dependent variable.

To test **hypothesis 2** (*The rate of decreasing hippocampal and cortical volumes, thinning of the cingulate and parahippocampal cortices, and changing hippocampal shape will be equal in DAT subjects that are untreated and in DAT subjects that are treated with donepezil alone, but greater than the rate of volume loss, thinning and hippocampal shape change in DAT subjects that are treated with the combination of donepezil and*

memantine.), rates of change for the various neuroanatomical variables will be compared in DAT subjects that are untreated, that are treated with donepezil alone, that are treated with the combination of donepezil and memantine, and in nondemented comparison subjects. These analyses will be performed using simple difference scores (follow-up minus baseline) for volume and thickness variables. To compare rates of change in hippocampal shape across groups, a MANOVA using eigenvectors derived from the time 1-to-time 2 transformation covariance will be performed (see above). The distributional characteristics of each of these variables will be examined prior to hypothesis testing. Finally, non-parametric (Wilcoxon rank sum tests) statistics will be used to compare the groups.

i. Sample Size and Power Considerations

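### The Hypothesis 2 shape test, as defined, measures hippocampal size and shape change together, so a difference in volume loss alone can make it reject

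*Combined protocol and SAP*

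**What the plan says.** Study Design section e (HDBM-LD) measures shape change by "mapping the transformations from the first time point onto the second time point via rigid-motion registration (rotation and translation"). It gives the no-change case as "If no change in the shape of the hippocampus has occurred, the result of this transformation is an identity map (modulo rotation and translation"), and then says that "any shape change that has occurred is defined as the deviation of the result of the transformation away from this identity map". No scale factor is removed at any step.

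Hypothesis 2, in the Specific Aims and again in section h, names as outcomes "The rate of decreasing hippocampal and cortical volumes, thinning of the cingulate and parahippocampal cortices, and changing hippocampal shape". Section h analyses volume by "simple difference scores (follow-up minus baseline) for volume and thickness variables". For shape, "a MANOVA using eigenvectors derived from the time 1-to-time 2 transformation covariance will be performed". Section h puts no hippocampal volume-change term in the shape test. The intracranial and cerebral volumes in section g are there to control for general brain volume reduction, which is a different quantity from hippocampal shrinkage, and section h does not bring them into the shape test.

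Preliminary Studies reports that, in the pilot longitudinal comparison, "eigenvector 1 was again correlated with the change in hippocampal volume across subject groups" (r = -0.75). Once volume change entered the logistic model, eigenvector 1 was no longer selected, while eigenvectors 2, 4 and 11 were. The Background says of the same study that "hippocampal shape change and the rate of volume loss provided complementary information".

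**The concern.** Rotation and translation preserve size. If a hippocampus shrinks by the same proportion everywhere, its shape is unchanged, yet every surface point is displaced after rigid alignment and the displacement is scored as shape change. The null hypothesis of the MANOVA is therefore that groups differ neither in size change nor in shape change. The label attached to it is shape alone.

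At stake is how a positive result is read. If combination treatment slowed volume loss and did nothing else, the volume test and the shape test would both tend to reject, and a reader could take one effect for two. The pilot checked the overlap by entering volume change in its logistic regression. The plan for Hypothesis 2 does not state that this check will be repeated.

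**Working it through.** **1. Reproducing the pilot figures (Preliminary Studies; 18 CDR 0.5, 26 CDR 0).**
- Shape MANOVA, F(12,31) = 2.66: tail probability 0.0141 (stated 0.014). T² = 2.66 × 12 × 42/31 = 43.25; D = √(43.25 × 44/(18 × 26)) = 2.02 (stated effect size 2.0).
- Volume ANOVA, F(1,42) = 7.81: p = 0.0078 (stated 0.008). Implied d = √(7.81 × (1/18 + 1/26)) = 0.857.

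The pilot shape and volume results are internally consistent.

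**2. Geometry.** Take the pilot left-sided loss of 164 from 1717 mm³ and suppose it were uniform. The linear factor is (1 − 164/1717)^(1/3) = 0.967, a 3.3% shrinkage. On a sphere of equal volume (radius 7.43 mm) that is about 0.24 mm inward at every point. Rigid alignment leaves this in place; removing one scale factor takes it to zero.

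**3. Rejection rate when groups differ only in volume loss.**

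Inputs:
- p = 12 eigenvectors, the number that explained 75% of variance in the pilot; section e retains about 75%.
- Volume effect d = 0.5, from section i.
- Share of that effect carried into the eigenvectors r = 0.75, from the pilot correlation.
- Group sizes from section a: about 40 on the combination, 38 (up to 47) on donepezil, 21 untreated.
- Two-sided .05. The plan states this for Hypothesis 1 only; it is assumed here for Hypothesis 2.

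Formula: two-group Hotelling test, noncentral F with 12 and n1 + n2 − 13 df, noncentrality λ = [n1·n2/(n1 + n2)] × (r·d)². Here (0.75 × 0.5)² = 0.1406.

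| Comparison | n1·n2/(n1 + n2) | λ | df2 | Rejection rate |
|---|---|---|---|---|
| 40 v 47 | 21.61 | 3.04 | 74 | 13.9% |
| 40 v 38 | 19.49 | 2.74 | 65 | 12.7% |
| 40 v 21 | 13.77 | 1.94 | 48 | 9.8% |

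**4. Upper bounds.** For 40 v 47, full loading (r = 1) at d = 0.5 gives 23%. The pilot effect of 0.857 gives 39% at r = 0.75 and 68% at r = 1. For 40 v 21 the corresponding figures are 15%, 23% and 42%.

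**5. Simulation check.** The surface was an ellipsoid, groups (40 v 47) differed only in uniform shrinkage, eigenvectors were kept to 75% of variance, and there were 300 runs per setting. At d = 0.5, rigid registration rejected 17–20% of the time; with scale removed, 5–7%. In these runs eigenvector 1 correlated with volume loss at about 0.8–0.9, above the reported 0.75, so the rigid rates sit between the r = 0.75 and r = 1 figures. The return to near 5% follows from making the difference purely uniform; it confirms the mechanism and says nothing about how common such a difference is.

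**The case against.** Much can be said for the plan, and most of it stands.

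- **Hypothesis 2 does not claim that shape is independent of volume.** Independence is claimed in Hypothesis 1, and section h addresses it there with a stepwise regression on all the neuroanatomical variables. A reader might infer that the investigators intend to count volume and shape as two separate confirmations. The documents do not say so. They do list and test the two separately without saying that one contains the other.
- **The measure is openly defined, and size-and-shape is a legitimate outcome.** This is so. The fault lies in the label and in what can be concluded from it. It does not make the MANOVA invalid.
- **A reader might infer that the shape result is volume under another name.** The pilot does not support this. Eigenvectors 2, 4 and 11 were selected with volume change in the model (χ² 19.4 without volume, 20.1 with it), and the shape effect of 2.0 (about 1.30 after bias correction) exceeds the volume effect of 0.86. The caption to Figure 2 also describes regional, not uniform, inward change. That was, however, a DAT-versus-control contrast, and it does not show that a difference between treatments would be free of volume.
- **The large rejection rates overstate the problem.** This is correct. An effect of 0.86 between treatments would equal the whole DAT-versus-control difference in the pilot, and r = 1 exceeds the observed correlation. Those figures are ceilings.
- **Removing scale has its own cost.** With localised loss, rescaling can push unaffected surface outward and weaken the real signal. In an illustrative ellipsoid with lateral-edge loss, volume-matched scaling cut the affected-area signal from 0.51 to 0.38 mm; least-squares scaling cut it only to 0.47 mm. Adjusting for concurrent volume change conditions on another outcome of treatment. Both are reasons to add an analysis and not to replace the planned one.

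**Conclusion.** The concern holds in a limited form. The no-change statement in section e is true only when hippocampal size is also unchanged. Because scale is not removed, the section h shape MANOVA tests size and shape change together and can reject on a volume-loss difference alone. At the plan's own effect size the rate is about 10–14% in place of 5%, a modest excess.

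These rates are illustrative. They rest on a two-group comparison (the plan has four groups), 12 eigenvectors, two-sided .05, and the use of the pilot correlation of 0.75, observed across both groups combined, as the share of the volume effect that enters the test. The direction does not depend on these choices. The documents do not support concluding that shape carries no information beyond volume, or that the rigid-registration analysis should be dropped.

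**What to change.** 1. Keep the rigid-registration MANOVA as planned, and call its outcome combined size-and-shape change in Study Design sections e and h.
2. Prespecify one companion analysis for Hypothesis 2: remove one least-squares uniform scale factor per hippocampus when aligning time 1 to time 2, recompute the eigenvectors from the scale-removed fields, and repeat the MANOVA.
3. State that a shape effect will be reported as separate from the volume effect only if the companion analysis supports it.
4. Optionally, enter hippocampal volume change in the post-hoc logistic regression, as the pilot did, and read it as descriptive because volume change is itself an outcome.

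The cost is one scaling step on surfaces already computed, one further decomposition, and wording changes in two sections. The scale-removed test is insensitive to uniform shrinkage and may slightly dampen localised loss, which is why the rigid analysis stays alongside it.

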A major objective during the first funding period was to test the hypothesis that an assessment of hippocampal structure could be used to predict the outcome of donepezil treatment in DAT patients. As proposed in our original application, estimates of cognitive decline over time were generated using CDR sum of-boxes scores, ADAS-Cog total scores, MMSE total scores and Neuropsychiatric Inventory (NPI) total scores (see Research Design and Methods section below for more description of these measures). Fifty-one subjects with DAT were included in this analysis and, to date, data were available for a minimum of 48 weeks in 38 subjects (this trial will be completed in the final year of the present funding period). In almost all cases, the subjects had been treated with donepezil, 10 mg/day, for the period of study – in rare subjects that could not tolerate this dose of donepezil, 5 mg/day, was used. In addition, we included data from 65 non-demented subjects (CDR 0) in the analysis, so that we could evaluate variation in hippocampal shape related to drug response in the context of normative structure. To estimate the rate of annual change in the selected clinical measures, a slope value was calculated for each subject using a growth curve model (Laird and Ware, 1982). The mean (SD) annual rate of change for the sum-of-boxes scores was 0.13 (± 0.11 , range -0.06 to +0.41) per year. Other mean (SD) annual rates of change were as follows: ADAS-Cog total score - 0.15 (± 0.29 , range -0.29 to +1.32); MMSE total score - -0.084 (± 0.17 , range - -0.61 to +0.16); the NPI total score - +0.027 (± 0.06 , range -0.03 to +0.37). Thus, in general, mild deterioration was observed in the DAT subjects

treated with donepezil (i.e., slopes for sum-of-boxes scores, ADAS-Cog and NPI scores were positive, while MMSE slopes were negative).

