A template image is prepared by an expert using manual outlining techniques, and includes, in this case, segmentation data for the total intracranial and brain volumes. The entire MR image of the template is first globally registered with the MR image of each target using a landmark-based transformation and scalar points at the boundaries of the brain and in the midline. An elastic transformation (with eight basis vectors having 2187 basis coefficients) is then performed, which matches the templates for the total intracranial space and total brain to the target. As with the transformations developed to study the hippocampus, the manifold and the elastic transformations used for this measurement are concatenated together and all the anatomical features of the segmented template brain are carried through the transformation.

h. Data Analysis

To test **hypothesis 1** (*Decreases in hippocampal and cortical volumes, thinning of the cingulate and parahippocampal cortices, and changes in hippocampal shape will be correlated with the rate of cognitive decline in subjects with very mild-to-mild DAT.*), growth curve models will be developed to assess the rate of cognitive decline for the principal (i.e., CDR sum-of-boxes scores) and secondary (i.e., ADAS-cog total scores, MMSE total scores, and NPI total scores) outcome variables (Laird and Ware, 1982). The underlying framework for the Laird and Ware model is essentially the same as for a traditional univariate repeated measures analysis of variance (ANOVA). However, the traditional ANOVA framework is difficult to apply when assessments are not available for all subjects at all time points. We have previously examined the advantages and disadvantages of this statistical model in characterizing rates of cognitive decline in a group of CDR 0.5 and CDR 1 DAT subjects highly similar to the one recruited for this project (Berg, et al, 1992). The CDR sum-of-boxes score was found to be entirely adequate as an outcome variable in that analysis (Berg, et al, 1992), because of its minimal ceiling and floor effects. The Laird and Ware model generates a slope value and intercept (i.e., estimate of baseline severity) for each subject.

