Based upon previous work by our group in similar groups of CDR 0.5 and CDR 1 DAT subjects (Berg, et al, 1988; Berg, et al, 1992), and on our experience with the subjects recruited and studied during the initial funding period, we estimate that the attrition rate of subjects who cannot continue in the study for the full two years due to pronounced deterioration, drug side-effects, or refusal to participate will be approximately 20% or less, leaving at least 40 subjects who would provide data for the entire two-year period. However, the number of subjects entered into the analysis may exceed this somewhat, since a slope value can be estimated for each subject who remains in the treatment trial for at least five assessments (one year). Estimating 40 subjects are used in the analysis used to test **Hypothesis 1**, we will have a power of .80 to detect a correlation (or partial correlation) of .44 or more with a 2-tailed significance level of .05 (Borenstein and Cohen, 1988; Kraemer and Thiemann, 1987).

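### Hypothesis 1 regresses growth-model slopes, unweighted, on MR change; if they are the model's predicted slopes, the MR coefficients are too small by an amount that the documents do not let one fix

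*Combined protocol and SAP*

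**What the plan says.** STUDY DESIGN, section h (Data Analysis) tests Hypothesis 1 in two stages. Growth curve models are first fitted to CDR sum-of-boxes (principal outcome) and to ADAS-Cog, MMSE and NPI (secondary). No MR measure is named in them. The output is described so: "The Laird and Ware model generates a slope value and intercept (i.e., estimate of baseline severity) for each subject".

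Those slopes are then related to MR change. Bivariate correlations "will be estimated using non-parametric statistics (Spearman's rho"). For independence, "a stepwise multiple regression model will be developed including all independent neuroanatomical variables and slope values for the CDR sum-of-boxes scores as the dependent variable". No weighting, slope standard error or reliability correction is mentioned.

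Unequal follow-up is expected. Section h prefers this model because "the traditional ANOVA framework is difficult to apply when assessments are not available for all subjects at all time points". Section i (Sample Size and Power Considerations) adds that "a slope value can be estimated for each subject who remains in the treatment trial for at least five assessments (one year"). Section i also gives power of 0.80 for a correlation or partial correlation of 0.44 with 40 subjects, two-sided 0.05. The preliminary donepezil study took its slopes the same way: "a slope value was calculated for each subject using a growth curve model".

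**The concern.** A subject's slope from a random-effects model is normally a predicted value: the subject's own data pulled toward the common mean, and pulled harder when there are fewer data. If the model producing it leaves out the MR measure, the common mean ignores that measure, and the pull removes part of the association that the second stage is meant to estimate. The second stage then gives a one-year slope the same weight as a two-year slope.

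At stake are the size of each MR coefficient in the regression and the realism of the power statement. Early leavers matter here because section i lists pronounced deterioration among the reasons for leaving; predicted slopes would make such subjects look more average than they are.

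**Working it through.** **Inputs from the documents.** n = 40, r = 0.44, two-sided 0.05, power 0.80, attrition about 20%, and one year as the minimum follow-up (section i). Visits at baseline, weeks 6 and 12, then every 12 weeks for two years (section a and flowchart), taken here as ending at week 96.

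**Assumption.** The reliability λ of a two-year slope (true slope variance divided by total slope variance) is not in the documents, which give no residual SD and no slope standard error. The range 0.3 to 0.9 is shown.

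**1. The plan's power figure.** Power = Φ(atanh(r)·√(n−3) − 1.96) = Φ(0.472 × 6.083 − 1.96) = Φ(0.91) = 0.82. With the Spearman variance factor 1.06 it is 0.80. The stated 0.80 reproduces.

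**2. Precision of short follow-up.** Slope sampling variance is the residual variance divided by Sxx, the sum of squares of time about its mean. In years, Sxx = 3.78 for weeks 0, 6, 12, 24, …, 96 and 0.63 for visits up to week 48. The ratio is 3.782/0.632 = 6.0.

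**3. Reliability at one year** (slope-only approximation). λ₁ = 1/[1 + 6.0(1−λ)/λ]. For λ = 0.9 this is 1/(1 + 5.98 × 0.111) = 0.60.

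**4. Regression coefficient.** A predicted slope keeps a fraction λ of a completer's true deviation from the mean and λ₁ of a one-year subject's. With 20% leaving at one year, the share of the coefficient recovered is roughly 0.8λ + 0.2λ₁; at λ = 0.9, 0.72 + 0.12 = 0.84. A simulation of the full intercept-and-slope model checks this (true correlation 0.44, 50 subjects, 10 leaving at week 48 at random, variance components known). It also fits the one-stage model with an MR-change-by-time term.

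| λ, two years | λ₁, one year | Hand approximation | Simulated, predicted slopes | Simulated, one-stage |
|---|---|---|---|---|
| 0.9 | 0.60 | 84% | 84% | 100% |
| 0.7 | 0.28 | 62% | 64% | 101% |
| 0.5 | 0.14 | 43% | 46% | 100% |
| 0.3 | 0.07 | 25% | 32% | 104% |

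With a true slope SD of 1, the SD of predicted slopes in leavers and completers was 0.72 and 0.93 (λ = 0.9), 0.50 and 0.84 (0.7), and 0.38 and 0.72 (0.5): the leavers are pulled in more. Separately fitted least-squares slopes gave coefficients of 0.44, 0.44 and 0.42 against about 0.44 at these three reliabilities; predicted slopes gave 0.37, 0.28 and 0.20.

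**5. Spearman's rho**, same setting, about 0.41 with true slopes. Predicted slopes gave 0.378, 0.327 and 0.269; least-squares slopes gave 0.376, 0.313 and 0.246. Both are attenuated, and shrinkage does not make it worse.

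**6. Power if 0.44 is the correlation with the true slope.** The observed correlation is 0.44√λ, put into the formula of step 1 with n = 40.

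| λ | Observed r | Power | n for 0.80 |
|---|---|---|---|
| 0.9 | 0.417 | 0.77 | 43 |
| 0.7 | 0.368 | 0.65 | 56 |
| 0.5 | 0.311 | 0.50 | 79 |
| 0.3 | 0.241 | 0.32 | 133 |

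The one-stage model with 50 subjects, 10 of them leaving at week 48, had power 0.86, 0.74, 0.56 and 0.38.

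**7. Null and informative dropout.** With no association and random dropout, the rank test on predicted slopes rejected in 4.5% and 5.3% of runs (λ = 0.7 and 0.3). When the fastest decliners left early, the predicted-slope coefficient fell to 0.35, 0.25 and 0.17 against 0.44 (λ = 0.9, 0.7, 0.5). A further simulation assumed slope SDs of 0.8 and 1.32 points per year and residual SDs of 1.0 and 1.5. Predicted slopes recovered 47–81% of the coefficient under random dropout, against 97–104% for one-stage. Under informative dropout the figures were 36–72% against 79–91%.

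**The case against.** The strongest reply is that the plan never calls its slopes predicted or shrunken. A five-assessment minimum would suit separately fitted slopes, and with those the coefficient is essentially unbiased. This stands as a limit on certainty. A per-subject slope generated by a Laird-Ware model is most naturally the predicted one, but that is an inference, and the unweighted mixing of one-year and two-year slopes is present under either reading.

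One could also say that 0.44 in section i means the correlation with the estimated slope. The 0.80 then stands, but the true correlation needed at reliability 0.7 is 0.44/√0.7 = 0.53. The plan does not say which is meant.

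Several stronger readings are tempting, and the documents or the calculations do not support them:

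- That shrinkage biases Spearman's rho. Step 5 shows that the loss comes from error in the slopes, so switching to raw slopes would not repair the correlation.
- That the second-stage test or its standard error is invalid. The slope is the dependent variable, so its error goes into the residual, and the null rejection rate was close to 5%.
- That a short slope has 12 times the variance of a full one. This comes from counting the first five flowchart visits, which end at week 36; section i equates the minimum with one year.
- That the narrow pilot slopes prove shrinkage. Reducing a true SD of 0.8–1.32 to the reported 0.11 would need a reliability of about 0.007–0.019. A different time unit would explain the figures as well.
- That Aim 1 is built around a points-per-year effect. It asks which measures correlate most strongly with progression and predict it independently.

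**Conclusion.** The point holds in a conditional form. The plan uses one growth-model slope per subject, unweighted, as the regression outcome and admits unequal follow-up. If the slopes are the model's predictions, each MR coefficient is biased toward zero: by about 16% at reliability 0.9, 36% at 0.7, 54% at 0.5 and 68% at 0.3. The direction was the same at every value tried. The size rests on an assumed reliability and on 20% leaving at one year.

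Under non-informative dropout the test of no association is sound; the harm is to effect size. Separately, error in the slopes lowers the power for a true correlation of 0.44, whichever kind of slope is used. It would go too far to conclude that the plan certainly shrinks its slopes, or that a one-stage model would gain power: no gain has been shown.

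**What to change.** Estimate and test each MR association inside the growth model already planned. Enter the MR change measure and its interaction with time, and report the interaction with its confidence interval, for CDR sum-of-boxes and for ADAS-Cog, MMSE and NPI. This weights subjects by the information they carry and removes the coefficient bias under non-informative dropout. Keep Spearman's rho as descriptive, and state whether the slopes used for it are predicted or separately fitted. Restate the power for r = 0.44 over a range of slope reliability.

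The cost is analysis-plan wording and slightly more modelling work, with no new data. The stated power will look less favourable. The one-stage model does not bring it back to 0.80 when reliability is low, and it only partly corrects for informative dropout.
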